Methocarbamol and Orphenadrine for Acute, Non-traumatic, Non-radicular Low Back Pain: A Randomized, Placebo Controlled, 3-armed Study

NCT#: NCT02665286 Protocol ID: 2015-5903 Version Date: 01/27/2016

[name] Professor and Vice-Chair for Clinical Investigations Department of Emergency Medicine Montefiore Medical Center Albert Einstein College of Medicine

Specific Aims

Low back pain (LBP) causes 2.4% of visits to US emergency departments (ED) resulting in 2.7 million visits annually. (1) In general, outcomes for these patients are unfavorable. One week after ED discharge, 70% of patients report persistent back-pain related functional impairment and 69% report analgesic use within the previous 24 hours.(2) Three months after the emergency visit, 48% of ED LBP patients report functional impairment, 42% report moderate or severe pain, and 46% report persistent analgesic use. (2)

It is not clear which medications should be prescribed for acute LBP. Non-steroidal anti-inflammatory drugs (NSAID) are more efficacious than placebo with regard to LBP relief, global improvement, and requirement of analgesic medication (3) but are insufficient treatment for as many as ½ of ED patients, who continue to suffer despite use of NSAIDs. Treatment of LBP with multiple concurrent medications is common in the ED--emergency physicians often prescribe skeletal muscle relaxants or opioids in combination with NSAIDs.(4) However, work recently completed has revealed that combining cyclobenzaprine, a skeletal muscle relaxant, or oxycodone/acetaminophen with an NSAID does not improve outcomes.(5) It remains uncertain if adding other skeletal muscle relaxants to NSAIDs improves LBP outcomes.

Two specific skeletal muscle relaxants, orphenadrine and methocarbamol, are each used in more than 250,000 U.S. ED visits for LBP annually, although scant evidence exists to determine the appropriateness of this approach.(6) Orphenadrine is centrally acting with prominent anti-cholinergic and anti-histaminic properties. Mechanism of action is not understood. Efficacy in low back pain may be related to non-specific analgesic properties. Mechanism of action of methocarbamol has also not been established. Its efficacy is thought to be related to CNS effects rather than direct effects on skeletal muscles.

Given the poor pain and functional outcomes that persist beyond an ED visit for acute LBP, we propose a clinical trial to determine whether combining either orphenadrine or methocarbamol with an NSAID is more effective than NSAID monotherapy for the treatment of acute, non-traumatic, non-radicular low back pain. Specifically, we will evaluate the following two hypotheses:

- 1) A daily regimen of naproxen + orphenadrine will provide greater relief of LBP than naproxen + placebo one week after an ED visit, as measured by the Roland Morris Disability Questionnaire
- A daily regimen of naproxen + methocarbamol will provide greater relief of LBP than naproxen + placebo one week after an ED visit, as measured by the Roland Morris Disability Questionnaire

Overview.

This will be a single center, double-blind, comparative effectiveness study, in which we enroll patients during an ED visit for musculoskeletal LBP and follow them by telephone seven days and three months later. Every patient will receive standard-of-care therapy, consisting of naproxen and a low back pain education session. Patients will be randomized to orphenadrine, methocarbamol, or placebo.

Subject selection:

Our goal is to include in this study a broad representation of patients with musculoskeletal back pain who are likely to respond to the investigational medications and who would not be considered candidates for spinal surgery or targeted epidural intervention. We hope for a widely generalizable study and therefore will not require diagnoses to be contingent on advanced imaging studies. Though we could ensure a more homogeneous study population by requiring imaging, we do not believe this is clinically useful and it will not facilitate dissemination and utilization of the study results. The presence or absence of palpable spasm of the paraspinal muscles will be recorded but not used as an entry criterion because the clinical significance and reliability of this finding is uncertain.(7)

Inclusion criteria:

-Present to ED primary for management of LBP, defined as pain originating between the lower border of the scapulae and the upper gluteal folds. Flank pain, that is pain originating from tissues lateral to the paraspinal muscles, will not be included.

- Absence of non-musculoskeletal etiology of low back, such as urinary tract infection, ovarian cysts, or influenza like illness. The primary clinical diagnosis, at the conclusion of the ED visit, must be a diagnosis consistent with non-traumatic, non-radicular, musculoskeletal LBP.

-Patient is to be discharged home. Patients admitted to the hospital are more likely to be treated with parenteral medication and therefore are not appropriate for this study.

- Age 18-69 Enrollment will be limited to adults younger than 70 years because of the increased risk of adverse medication effects in the elderly.

-Non-radicular pain: pain cannot radiate below the gluteal folds in a radicular pattern. Patients with non-radicular pain extending below the gluteal folds will not be excluded

-Pain duration ≤ 2 weeks (336 hours). Patients with more than two weeks of pain are at increased risk of poor pain and functional outcomes.(2)

-Prior to the acute attack of LBP, back pain cannot have occurred once per month or more frequently. Patients with more frequent back pain are at increased risk of poor pain and functional outcomes.(2)

-Non-traumatic LBP: no substantial and direct trauma to the back within the previous month -Functionally impairing back pain: A baseline score of > 5 on the Roland-Morris Disability Questionnaire (Appendix)

Exclusion criteria:

-Not available for follow-up

-Pregnant or breast-feeding

-Chronic pain syndrome defined as use of any analgesic medication on a daily or near-daily basis -Allergic to or intolerant of investigational medications

-Contra-indications to non-steroidal anti-inflammatory drugs: 1) history of hypersensitivity to NSAIDs or aspirin or patients in whom NSAIDS or aspirin have induced allergic manifestations such as asthma, nasal polyps, rhinitis, or urticarial 2) active or history of peptic ulcer disease, chronic dyspepsia, or active or history of gastrointestinal bleed 3) Severe heart failure (NYHA 2 or worse) 4) hypertension (JNC7 stage 2 or worse) 5) Chronic kidney disease 3 or worse 6) Current use of anti-coagulants, bleeding with tooth brushing, easy bruisability 7) Hepatitis 8) Alcoholism

Naproxen plus orphenadrine or methocarbamol for LBP. An RCT. Version 012716

-Contra-indications to orphenadrine: 1) Glaucoma, Prostatic hypertrophy, Myasthenia gravis, Pyloric or duodenal obstruction

-Contra-indications to methocarbamol: 1) Myasthenia gravis, Chronic kidney disease 3 or worse

Study arms:

- A. The orphenadrine arm: Naproxen 500mg, orally twice per day + orphenadrine 100mg, orally twice per day
- B. The methocarbamol arm: Naproxen 500mg tablets, orally twice per day + methocarbamol 750mg, orally as 1 or 2 tabs, thrice per day
- C. The control arm: Naproxen 500mg tablets taken twice per day + placebo. Placebo dose will be either 1 capsule orally twice per day or 1 or 2 capsules orally, thrice per day

In an effort to maximize effectiveness while minimizing side effects, patients will be instructed to take one or two pills of the methocarbamol every 8 hours. If one tablet of the methocarbamol affords sufficient relief then there will be no need for the patient to take the second tablet. However, if the patient has not experienced sufficient relief within 30 minutes of taking one investigational medication tablet, they will be instructed to take the second tablet. Orphenadrine is only manufactured in 100mg extended release tablets and is therefore not amenable to flexible dosing. All study patients will be given 14 naproxen tablets, a seven day supply, and a sufficient number of investigational tablets to last 7 days. Optimal dosing of methocarbamol has not been established. We believe the dosing regimen we chose is sufficient to determine efficacy while not exposing patients to unnecessary risk.(8-10)

Outcome measures

1. Roland Morris LBP Disability Questionnaire (RMDQ)--Reproduced in the Appendix. This 24-item LBP functional scale is recommended for use in LBP research.(11) Its yes/ no format is amenable to telephone follow-up. We have used it successfully to obtain post-ED follow-up in five previous LBP studies involving more than 1500 patients.

2. Ordinal pain scale ("severe", "moderate", "mild", or "none"). Study participants will be asked to describe their worst back pain in the previous 24 hours.

3. Medication requirements: "Did you require any medication to treat your low back pain in the previous 24 hours?"

4. Low back pain frequency: "Over the last 24 hours, how often were you in pain? Not at all, Rarely, Sometimes, Usually, Always". Low back pain symptomatology is quite variable. Some patients may experience no pain unless they move a certain way. Others may experience a constant low level of pain. This question will help determine the burdensomeness of the LBP in the patient's daily life.5. Satisfaction, as measured by response to this question: The next time you go to the ER with low back pain, do you want to get the same combination of medications?

Baseline measures

1. Roland Morris LBP disability questionnaire

2. Patient Health Questionnaire depression module, the PHQ 9, will be assessed at the baseline visit.

3. 5-item Cassandra questionnaire. These five questions, based on psychological variables, predict poor outcomes in an emergency room population.(12) (Reproduced in the Appendix)

4. Perceived risk of not recovering. Pain outcomes may be influenced by expectations. After providing an educational intervention, we will ask study participants to estimate how long they believe they will continue to suffer from pain.

Naproxen plus orphenadrine or methocarbamol for LBP. An RCT. Version 012716

5. StarT Back LBP questionnaire

Primary outcome

The change in Roland Morris scale between the baseline ED visit and the one week follow-up (Roland-Morris _{baseline} - Roland-Morris _{1week}). The baseline questions will refer to the time period immediately prior to ED presentation (Before you came to the ER today, were you able to....)..

Secondary outcomes

- The following outcomes will be assessed one week after ED discharge
- 1. Day post ED discharge able to return to all usual activities
- 2. Satisfaction with treatment
- 3. Number of visits to any healthcare provider.

4. Worst LBP over the previous 24 hours, using a four point ordinal scale: severe, moderate, mild, or none and a 0 - 10 verbal integer scale

5. Use of any analgesic or LBP medication within the previous 24 hours.

6. Frequency of low back pain using the five point Likert scale: Not at all, Rarely, Sometimes, Usually, Always

7.Absolute RMDQ score

The following outcomes will be assessed three months after ED discharge

1. Roland Morris Disability Questionnaire

2. Worst LBP over the previous week, using a four point ordinal scale: severe, moderate, mild, or none and a 0 - 10 verbal integer scale

3. Frequency of low back pain over the previous week using the five point Likert scale: Not at all, Rarely, Sometimes, Usually, Always

- 4. Number of days with LBP since ED discharge
- 5. Use of any analgesic or LBP medication within the previous 7 days.
- 6. Number of visits to any healthcare provider.
- 7. Satisfaction with medication and with the current state of the LBP

Adverse events

The following adverse medication effects will be assessed at the one week follow-up.

-CNS side effects including drowsiness and dizziness

-GI side effects including dyspepsia, nausea, and bleeding

-All other side effects

Randomization and blinding

The pharmacist will perform randomization in blocks of 6 based on a sequence generated at http://randomization.com. Every block of six will contain two orphenadrine assignments, two methocarbamol assignments, one placebo assignment dosed as 1 capsule twice daily (to mirror orphenadrine dosing), and one placebo assignment dosed as 1-2 capsules thrice daily (to mirror methocarbamol dosing). Therefore, though patients will not know whether they have been assigned to active medication or placebo, they may deduce to which medication they were not assigned. This does not threaten the internal validity of the study because patients will not know whether or not they received active medication.

Naproxen will not be masked. Orphenadrine, methocarbamol, and placebo will be masked by placing tablets into identical capsules, which will be packed with scant amounts of lactose and sealed. This masking will take place in a secure location inaccessible to ED personnel. Patients will be presented with two vials of medication. The vial containing the naproxen will be labeled in a typical manner. The second vial, containing orphenadrine, methocarbamol, or placebo will be labeled as investigational medication. Patients will be instructed to the investigational medication only as needed for moderate or severe LBP.

Details of protocol

Prior to discharge from the ED and after the patient's pain has been controlled, the attending emergency physician will refer appropriate patients to study personnel for screening. Eligible patients would have already received different and various medications in the ED for their pain (potentially including naproxen) prior to being approached for study participation. This decision is up to the attending physician and is not related to participation in the study. Patients will be screened and consented. Research associates will ascertain baseline socio-demographic information, low back pain history, and baseline variables discussed above. A urine pregnancy test will be performed. Research personnel will provide each patient with a 15-minute educational intervention. This will be based on NIAMS's Handout on Health: Back Pain information webpage (available at http://www.niams.nih.gov/Health Info/Back Pain/default.asp) Research personnel will review each section of the information sheet with the patient and elicit questions. Patients will be discharged with two medical vials, one containing naproxen and one containing placebo, orphenadrine, or methocarbamol. Patients will be cautioned not to take off protocol LBP medications without first consulting with a healthcare provider. Patients will be cautioned not to drink alcohol or use other centrally-acting substances while using study medications. Patients will be cautioned not to drive after taking the study medications. Follow-up phone calls will be conducted one week and three months after ED discharge. Follow-up will be attempted daily until successful. For patients difficult to contact, express courier or home visit will be used to obtain follow-up information. Analysis. An intention-to-treat analysis will be performed. The primary outcome will be a comparison of the change in RMDQ between baseline and one week. Results will be reported as means with 95%CI. A t-test for independent samples will be used to determine statistically significant differences

between placebo and each of the active medications. Secondary outcomes will be reported as rates with 95%CI. A per protocol efficacy analysis will be conducted among those patients who use the investigational medication at least once.

Sample size calculation

We based assumptions on a recently completed RCT of LBP treatment. The mean improvement in RMDQ among those who receive naproxen alone was 10.2. The standard deviation was 8.9. A widely accepted minimum clinically important improvement of 5 points on the RMDQ would require those randomized to active medication to demonstrate a mean improvement of 15.2 on the RMDQ. Using a standard alpha of 0.05 and a beta of 0.20, we determined the need for 50 subjects in each arm. To account for protocol violations and patients lost-to-follow-up (typical lost-to-follow-up rate is 5%) and to ensure sufficient power for the per protocol analysis (in our previous ED-based LBP studies, up to 1/3 of enrolled patients have not used the medication more than once), we intend to enroll 80 patients in each arm.

Data Safety Monitoring Committee. This committee will be headed by [name] and include XXX. The committee will meet every month with the PI to 1) monitor adverse events and develop strategies to minimize these; and, 2) monitor recruitment and enrollment. There will not be an interim analysis. Naproxen plus orphenadrine or methocarbamol for LBP. An RCT. Version 012716 6

Registration. The study will be registered at http://www.clinicaltrials.gov.

Consent. Study personnel will obtain informed consent once the patient's pain has been controlled and the patient is ready for discharge from the ED.

Risks/Benefits

Non-steroidals are used in 50% of more than 2.5 million annual US ED visits for LBP. Skeletal muscle relaxants are used in 43% of these visits. Regardless of results, this study will have a national impact. Study subjects will benefit by receiving a medication that is likely to improve their acute LBP. In addition to breach of confidentiality, which is unlikely, and inconvenience to the subject, which will undoubtedly occur, it is likely that subjects will experience adverse medication effects. For the most part, these are nuisance events. Skeletal muscle relaxants such as orphenadrine and methocarbamol are generally well tolerated but can cause substantial drowsiness and when combined with alcohol or other centrally acting substances may be lethal. Non-steroidals can cause life-threating gastro-intestinal bleeding, but this is unlikely in patients screened for gastro-intestinal illness who will take the medication for one week only.

Data Storage & Confidentiality

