Appendix 1. Roland Morris low back pain disability questionnaire

1.	Over the last 24 hours. I have staved home most of the time because of my healt paint	No ⁰	Yes ¹
	Over the last 24 hours, I have stayed home most of the time because of my back pain:		
2.	Over the last 24 hours, I changed position frequently to try to get my back comfortable:	No ⁰	Yes ¹
3.	Over the last 24 hours, I walked more slowly than usual because of my back:	No ⁰	Yes ¹
4.	Over the last 24 hours, I have not been doing any jobs that I usually do around the house	No^0	Yes ¹
	because of my back pain:		
5.	Over the last 24 hours, I used a handrail to get upstairs because of my back pain:	No ⁰	Yes ¹
6.	Over the last 24 hours, I lay down to rest more often because of my back pain:	No ⁰	Yes ¹
7.	Over the last 24 hours, I have had to hold on to something to get out of an easy chair	No^0	Yes ¹
	because of my back pain		
8.	Over the last 24 hours, I have tried to get other people to do things for me because of my	No^0	Yes ¹
	back pain:		
9.	Over the last 24 hours, I got dressed more slowly than usual because of my back pain:	No ⁰	Yes ¹
10.	Over the last 24 hours, I only stood up for short periods of time because of my back pain:	No ⁰	Yes ¹
11.	Over the last 24 hours, I tried not to bend or kneel down because of my back pain:	No^0	Yes ¹
12.	Over the last 24 hours, I found it difficult to get out of a chair because of my back pain:	No^0	Yes ¹
13.	Over the last 24 hours, my back was painful almost all of the time:	No ⁰	Yes ¹
14.	Over the last 24 hours, I found it difficult to turn over in bed because of my back pain:	No ⁰	Yes ¹
15.	Over the last 24 hours, my appetite was not very good because of my back pain:	No^0	Yes ¹
16.	Over the last 24 hours, I have had trouble putting on my socks (or stockings) because of	No ⁰	Yes ¹
	the pain in my back or leg:		
17.	Over the last 24 hours, I could only walk short distances because of my back pain:	No ⁰	Yes ¹
18.	Over the last 24 hours, I slept less well because of my back:	No ⁰	Yes ¹
19.	Over the last 24 hours, I got dressed with the help of someone else because of my back	No ⁰	Yes ¹
	pain:		
20.	Over the last 24 hours, I sat down for most of the day because of my back:	No^0	Yes ¹
21.	Over the last 24 hours, I avoided heavy jobs around the house because of my back pain:	No ⁰	Yes ¹
22.	Over the last 24 hours, I was more irritable and bad tempered with people than usual	No ⁰	Yes ¹
	because of my back pain,		

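### Both hypotheses promise pain relief but are tested on a functional scale, and no matching pain score is on the baseline list

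*Combined protocol and SAP*

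**What the plan says.** In Specific Aims, the first hypothesis states: "A daily regimen of naproxen + orphenadrine will provide greater relief of LBP than naproxen + placebo one week after an ED visit". With the instrument included, each of the two hypotheses claims "greater relief of LBP than naproxen + placebo one week after an ED visit, as measured by the Roland Morris Disability Questionnaire" (the wording is identical apart from the active drug).

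Under Outcome measures the RMDQ is described as follows: "This 24-item LBP functional scale is recommended for use in LBP research". The Primary outcome section defines the endpoint as "The change in Roland Morris scale between the baseline ED visit and the one week follow-up". The Analysis text in Details of protocol applies an independent-samples t-test to that change, placebo against each active drug. The sample size rests on the same scale.

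Pain is measured separately. The one-week secondary outcomes include "Worst LBP over the previous 24 hours, using a four point ordinal scale" together with a 0-10 verbal scale, and a five-level frequency item. Both recur at three months with a one-week recall period. The Analysis text says that secondary outcomes will be reported as rates with 95% confidence intervals.

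The Baseline measures list opens with "1. Roland Morris LBP disability questionnaire", followed by the PHQ-9, the Cassandra items, expected time to recovery and the StarT Back questionnaire. No pain-intensity or pain-frequency item appears there. Details of protocol adds that a low back pain history is taken, without saying what it contains.

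**The concern.** The protocol treats pain and function as different outcomes elsewhere. Specific Aims reports them side by side for three months after the emergency visit: 48% with functional impairment and 42% with moderate or severe pain. The hypotheses then use the language of pain for a result on function. If the trial report follows the hypotheses, a difference in RMDQ, or its absence, will be stated as a finding about pain relief, although that finding belongs to the secondary pain scales.

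Those pain scales are also planned more thinly than they could be. On the listed measures, no patient's change in pain can be calculated, and week-one pain cannot be adjusted for its own starting value. Nor is a between-arm comparison of mean 0-10 pain specified, since secondary outcomes are to be reported as rates. A baseline score that was not collected at enrolment cannot be reliably recovered later.

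**Working it through.** **1. Does the plan hang together on the RMDQ?** Inputs from Sample size calculation: difference 15.2 − 10.2 = 5 points, SD 8.9, alpha 0.05 (taken as two-sided), power 0.80.

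n per arm = 2 × (1.960 + 0.842)² × 8.9² / 5² = 2 × 7.849 × 79.21 / 25 = 49.7, so 50.

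This reproduces the stated 50 per arm. (The t-distribution version gives 50.7; a one-sided test gives 40 and does not match.) Allowing for 5% loss and one third not using the drug, 50 / (0.95 × 2/3) = 78.9, in line with the planned 80. Hypothesis, endpoint, test and sample size therefore all use the same measure. The mismatch lies in what that measure is called.

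**2. What does the RMDQ ask?** From Appendix 1, item by item:
- One item asks about pain directly, item 13: "Over the last 24 hours, my back was painful almost all of the time".
- Nineteen others ask about an activity, limitation, sleep position, appetite or mood that the patient attributes to pain.
- Four (items 2, 3, 18 and 20) refer to the back without naming pain.

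So 1 + 19 = 20 of 24 items name pain, but 23 of 24 score something other than the presence of pain. The scale measures disability due to back pain, which agrees with the protocol's own description.

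**3. Which measures have a baseline?**

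| Measure | Baseline list | One week | Three months |
|---|---|---|---|
| RMDQ | yes | yes | yes |
| Worst pain, ordinal | no | yes | yes |
| Worst pain, 0-10 | no | yes | yes |
| Pain frequency | no | yes | yes |

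**4. What would a baseline pain score add?** Evaluable per arm: 80 × 0.95 = 76. For a two-sided t-test at 0.05 with 80% power on week-one pain alone, the detectable standardised difference is 0.457. (The normal approximation, 2.802 × √(2/76), gives 0.455.) Adjusting for a baseline score with within-arm correlation ρ multiplies the variance by 1 − ρ² and the detectable difference by √(1 − ρ²). The documents give no ρ, so a range is shown:

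| Assumed ρ | Variance removed (ρ²) | Detectable standardised difference |
|---|---|---|
| none (no baseline) | 0% | 0.46 |
| 0.2 | 4% | 0.457 × 0.980 = 0.45 |
| 0.3 | 9% | 0.457 × 0.954 = 0.44 |
| 0.5 | 25% | 0.457 × 0.866 = 0.40 |
| 0.6 | 36% | 0.457 × 0.800 = 0.37 |

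The documents give no SD for the 0-10 scale, so these cannot be converted to scale points.

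**The case against.** The strongest reply is that nothing in the plan is invalid. Each hypothesis names its instrument in the same sentence, the protocol openly calls that instrument functional, and eligibility requires functional impairment on it. This stands. A reader might infer that the trial can neither support nor refute its hypotheses; the documents do not support that, because as operationalised both are directly testable by the planned analysis.

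Four further inferences also go too far.
- *That week-one pain cannot be compared without a baseline.* Randomisation makes the arms comparable, and the test and interval already allow for chance imbalance.
- *That only one RMDQ point has to do with pain.* Twenty of 24 items name it.
- *That sedation would pull pain and RMDQ apart.* The relevant items (3, 6 and 24) count slow walking, lying down or staying in bed only when attributed to the back or back pain. The documents offer no evidence of such a divergence.
- *That no baseline pain data will exist at all.* The documents show only that none is listed. The back pain history is unspecified, and the StarT Back questionnaire is not reproduced.

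It is also fair to say that the precision gain is modest and rests on assumed correlations, and that baseline RMDQ could serve as a covariate and recover some of it.

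What these replies do not remove is the label. Naming the instrument makes the claim testable, but it does not turn a functional score into a measure of pain relief.

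**Conclusion.** The point holds as a low-cost improvement, not as a flaw that invalidates the trial. The primary result will be about function related to low back pain, while the hypotheses describe it as relief of pain. The pain outcomes are validly comparable between arms but, on the listed measures, lack a matching baseline. The loss is limited to within-patient change in pain and to precision: a detectable standardised difference of about 0.46 instead of 0.44 (correlation 0.3) or 0.40 (correlation 0.5).

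These figures assume 76 evaluable patients per arm, a two-sided 0.05 test, 80% power, and a linear relation between baseline and week-one pain. The correlations are assumptions. If the unspecified back pain history already contains a matching pain score, the second half of the point reduces to naming it in the plan and using it.

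**What to change.** 1. Reword both hypotheses, and the conclusion to be drawn from the primary analysis, to *greater improvement in LBP-related functional impairment, as measured by the RMDQ*. Reserve statements about pain for the pain scales.
2. Add three items to the Baseline measures: worst pain on the ordinal scale, worst pain on the 0-10 scale, and pain frequency. Use the one-week wording and the anchor already set for the baseline RMDQ, the period just before arrival at the emergency department. The anchor matters because patients are approached only after their pain has been controlled, so a score of current pain would reflect treatment already given.
3. State in the Analysis text that mean week-one 0-10 pain will be compared between placebo and each active arm, adjusted for its baseline value, with a 95% confidence interval.

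The cost is about a minute of extra questions per patient, a few sentences of text, and a narrower primary claim. The primary endpoint, its t-test and the sample size of 80 per arm do not change.

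### The quoted question for low back pain frequency does not name the back, so pain from other sites may be recorded in this secondary outcome

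*Combined protocol and SAP*

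**What the plan says.** Outcome measures, item 4, carries the heading of low back pain frequency and gives one question in quotation marks: "Over the last 24 hours, how often were you in pain", answered in five categories from *Not at all* to *Always*. The explanation that follows says "This question will help determine the burdensomeness of the LBP in the patient's daily life".

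Two secondary outcomes correspond to this item. At one week (Secondary outcomes, one-week list, item 6) it is "Frequency of low back pain using the five point Likert scale". At three months (three-month list, item 3) it is "Frequency of low back pain over the previous week using the five point Likert scale". No patient-facing wording is given for the three-month version.

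The neighbouring items in Outcome measures do name the site. For item 2, "Study participants will be asked to describe their worst back pain in the previous 24 hours". Item 3 asks "Did you require any medication to treat your low back pain in the previous 24 hours".

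**The concern.** A question given word for word is likely to be read out as written. Read literally, this one asks about pain anywhere. A patient with a recovered back and a headache or an upset stomach could truthfully give an answer other than *Not at all*, and nothing in the recorded response would show that the back was not the source. The documents contain no instruction to the interviewer to confine the answer to the back.

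What is at stake is how closely one secondary outcome measures what its definition says. The item is intended to show how burdensome the back pain is, and answers about other pain blur that.

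**Working it through.** **1. The item against its own definitions.**

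| Place | Site named? | Window |
|---|---|---|
| Outcome measures, item 4, heading and stated purpose | Low back | none given |
| Outcome measures, item 4, quoted question | No | 24 hours |
| Secondary outcomes, one week, item 6 | Low back | none given |
| Secondary outcomes, three months, item 3 | Low back | previous week |

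The quoted question is the only entry without a site.

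**2. The item against its neighbours.** In Outcome measures, item 2 (worst pain), item 3 (medication) and item 5 (satisfaction) all refer to the back or low back. In Appendix 1, each of the 24 Roland-Morris items mentions the back; item 16 mentions back or leg. The omission in item 4 is therefore out of step with the plan's own practice.

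**3. Whether other pain can be present.** The relevant exclusion is "Chronic pain syndrome defined as use of any analgesic medication on a daily or near-daily basis". This removes patients with frequent analgesic use, but it leaves in those with intermittent pain elsewhere. The Adverse events section expects dyspepsia among the side effects to be assessed at one week, and one of the baseline questions in Appendix 2 concerns chest pain. Other pain is possible; the documents give no rate for it.

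**4. What depends on the item.** The primary outcome is the change in Roland-Morris score and does not use this question. The plan's only calculated figure is for that outcome. With a difference of 5, SD 8.9, alpha 0.05 (two-sided assumed) and power 0.80:

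n per arm = 2 × (1.960 + 0.842)² × 8.9² / 5² = 2 × 7.85 × 79.21 / 25 ≈ 49.7, rounded up to 50.

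This agrees with the stated 50 per arm (power at 50 is 80.2%), and nothing in it changes if the question is reworded.

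**5. Direction and form of the effect.** Suppose, as an assumption, that the outcome is analysed as the proportion answering *Not at all*. Let p be the true proportion free of low back pain in an arm, and q the share of those patients who report other pain instead. The observed proportion is p(1 − q). With the same q in both arms the observed difference is

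(p₁ − p₂)(1 − q).

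For an assumed true difference of 15 percentage points:

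- q = 10%: 15 × 0.90 = 13.5 points
- q = 30%: 15 × 0.70 = 10.5 points

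The 15 points, the range for q and the cut at *Not at all* are all assumptions. The Analysis paragraph says only that secondary outcomes are reported as rates with confidence intervals, and sets no cut for this five-category scale. With a cut between *Sometimes* and *Usually*, for example, a patient with a recovered back who answers *Rarely* because of an occasional headache would not be misclassified.

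**The case against.** The strongest reply is context. These patients were enrolled for low back pain and are contacted about it, and the follow-up includes the Roland-Morris questionnaire and other back-specific questions. Many will take the question to mean the back without being told. The heading, the stated purpose and both outcome definitions all say low back pain. The operational telephone script is not among the documents, so a lead-in that supplies the site may exist. Back-specific measures also sit alongside: worst low back pain at both follow-ups, days with low back pain at three months, and Roland-Morris item 13 on near-constant back pain.

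Most of this stands, and it limits the point. A reader might infer from the wording that pain from any site is counted as the outcome. The documents do not support that: no rule counts non-back pain, and the definitions say the opposite. The supported statement is that such pain may be recorded for some patients.

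A reader might also see a contradiction between the 24-hour question and the previous-week outcome, or expect the harm to be greatest at three months. Neither follows. The three-month list sets its own longer windows for worst pain, frequency and medication alike, so the quoted question reads as the one-week form. The wording of the three-month question is not given and cannot be said to omit the back.

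Context does not, however, justify leaving the site out of a question whose neighbours state it. Once collected, ambiguous answers cannot be sorted by site.

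**Conclusion.** The point holds as a minor wording defect. The question quoted for low back pain frequency does not name the back, while its heading, its purpose, its neighbours and both outcome definitions do. Non-back pain may therefore enter this one secondary outcome.

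If that happens equally often in all arms, the result is noise and a diluted difference, not a false benefit. Equality across arms is itself an assumption; the documents give nothing to test it. The amount cannot be computed from the documents, which supply neither a rate of other pain nor expected values for this outcome. The reductions worked above show the form of the effect and should not be read as an estimate of it. The primary outcome and the planned sample size are unaffected.

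**What to change.** Name the low back in the question. At one week: *Over the last 24 hours, how often did you have low back pain?* At three months, use the same wording with the window already stated for that visit: *Over the last week, how often did you have low back pain?* The response categories stay as they are.

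The cost is a few words in the protocol and the telephone script. Design, sample size and analysis do not change. The change is best made before the first follow-up call, because earlier answers could not be corrected. If the form in use already names the back, only the protocol text needs correcting.
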